## ***2.5 Variables***

### ***2.5.1 Outcome measure***

The primary outcome of this study is IAPI in patients who underwent surgery procedure. IAPI is a localized skin injury caused by the prolonged action of pressure, friction, and (or) shear forces during surgery, most occurring within 1-3 days postoperatively, and also within 6 days postoperatively. The severity of pressure injuries is classified using the National Pressure Ulcer Advisory Panel Pressure Injury Staging System:

- Stage 1 Pressure Injury: The skin is intact with erythema that does not change white in local acupressure.***

Intact skin with a localized area of nonblanchable erythema, which may appear differently in darkly pigmented skin. Presence of blanchable erythema or changes in sensation, temperature, or firmness may precede visual changes. Color changes do not include purple or maroon discoloration; these may indicate deep tissue pressure injury.

- ***Stage 2 Pressure Injury: Partial-thickness skin loss with exposed dermis.***

Partial-thickness loss of skin with exposed dermis. The wound bed is viable, pink or red, moist, and may also present as an intact or ruptured serum-filled blister. Adipose (fat) is not visible and deeper tissue is not visible. Granulation tissue, slough and eschar, are not present. These injuries commonly result from adverse microclimate and shear in the skin over the pelvis and shear in the heel.

- ***Stage 3 Pressure Injury: Full-Thickness Skin Loss***

Full-thickness skin loss, in which adipose (fat) is visible in the ulcer and granulation tissue and epibole (rolled wound edges), is often present. Slough and/or eschar may be visible. The depth of tissue damage varies by anatomical location; areas of significant adiposity can develop deep wounds. Undermining and tunneling may occur. Fascia, muscle, tendon, ligament, cartilage, or bone is not exposed. If slough or eschar obscures the extent of tissue loss, this is an unstageable pressure injury.

- ***Stage 4 Pressure Injury: Full-Thickness Skin and Tissue Loss***

Full-thickness skin and tissue loss with exposed or directly palpable fascia, muscle, tendon, ligament, cartilage, or bone in the ulcer. Slough and/or eschar may be visible. Epibole (rolled edges), undermining, and/or tunneling often occur. Depth varies by anatomical location. If slough or eschar obscures the extent of tissue loss, this is an unstageable pressure injury.

- ***Unstageable Full-Thickness Pressure Injury: Obscured Full-Thickness Skin and Tissue Loss***

Full-thickness skin and tissue loss in which the extent of tissue damage within the

ulcer cannot be confirmed because it is obscured by slough or eschar. If slough or eschar is removed, a Stage 3 or Stage 4 pressure injury will be revealed. Stable eschar (ie, dry, adherent, intact without erythema or fluctuance) on ischemic limb or heels should not be softened or removed.

- ***Deep Tissue Pressure Injury: Persistent Nonblanchable Deep Red, Maroon or Purple Discoloration***

Intact or nonintact skin with localized area of persistent nonblanchable deep red, maroon, purple discoloration, or epidermal separation revealing a dark wound bed or blood-filled blister. Pain and temperature change often precede skin color changes. Discoloration may appear differently in darkly pigmented skin. This injury results from intense and/or prolonged pressure and shear forces at the bone-muscle interface. The wound may evolve rapidly to reveal the actual extent of tissue injury or may resolve without tissue loss. If necrotic tissue, subcutaneous tissue, granulation tissue, fascia, muscle, or other underlying structures are visible, this indicates a full-thickness pressure injury (unstageable, Stage 3, or Stage 4). Do not use DTPI to describe vascular, traumatic, neuropathic, or dermatologic conditions.

- ***Medical Device–Related Pressure Injury***

Medical device–related pressure injuries result from the use of devices designed and applied for diagnostic or therapeutic purposes. The resultant pressure injury generally conforms to the pattern or shape of the device. The injury should be staged using the staging system.

### ***2.5.2 Secondary outcome***

The secondary outcome of this study is in-hospital mortality, which refers to the number of patients who die from any cause while receiving surgical procedure in a hospital. The data from a large sample of 13,254 patients in 1117 ICUs across 90 countries revealed that patients with pressure injuries (PI) exhibited a significantly higher mortality rate compared to those without PI. Furthermore, there was a gradual increase in the correlation between the severity of pressure injury and mortality rate.

Surgical site infections (SSIs) will also be observed, SSIs are infections of the incision or organ or space that occur after surgery. Sepsis is defined as life-threatening organ dysfunction caused by a dysregulated host response to infection, the subsequent statement presents the diagnostic criteria in accordance with the Third International Consensus Definition of sepsis:

- Organ dysfunction can be identified as an acute change in total Sequential Organ Failure Assessment (SOFA) score  $\geq 2$  points consequent to the infection.
  - The baseline SOFA score can be assumed to be zero in patients not known to have preexisting organ dysfunction.
  - An ASOFA score  $\geq 2$  reflects an overall mortality risk of approximately 10% in a general hospital population with suspected infection. Even patients presenting with modest dysfunction can deteriorate further, emphasizing the seriousness of this condition and the need for prompt and appropriate intervention, if not already being instituted.
- In lay terms, sepsis is a life-threatening condition that arises when the body's

response to an infection injures its own tissues and organs.

- Patients with suspected infection who are likely to have a prolonged ICU stay or to die in the hospital can be promptly identified at the bedside with quick SOFA, ie, alteration in mental status, systolic blood pressure  $\leq 100$  mmHg, or respiratory rate  $\geq 22$ /min.
- Septic shock is a subset of sepsis in which underlying circulatory and cellular/metabolic abnormalities are profound enough to substantially increase mortality.
- Patients with septic shock can be identified with a clinical construct of sepsis with persisting hypotension requiring vasopressors to maintain mean arterial pressure (MAP)  $\geq 65$  mmHg and having a serum lactate level  $> 2$  mmol/L (18 mg/dL) despite adequate volume resuscitation. With these criteria, hospital mortality is in excess of 40%.

The surgical complications in patients during the same hospitalization will also be observed, as defined by the Clavien-Dindo classification. Additionally, we evaluated the duration of hospital stay and associated costs incurred by patients within this hospitalization period.

### ***2.5.3 Predictors***

Physiological observation indicators for all surgical patients were recorded as actual observed values within the first 24 hours preoperative, while other intraoperative observation indicators (such as anesthesia method, body temperature, blood pressure,

surgical time, blood loss, etc.) were documented based on actual observations during surgical procedures. Data collection was conducted independently using commonly employed scales for these observation indicators (Table 1):

Clearly define all outcomes, exposures, predictors, potential confounders, and effect modifiers. Give diagnostic criteria, if applicable

### ***2.6 Follow-up period***

The clinical follow-up will be conducted at 0.5, 2-, 24-, 48-, 72-hours and 7 days post-surgery, as well as at the three-month mark following the completion of the surgical procedure during in-hospital. The investigator has the flexibility to carry out these follow-ups either through telephone communication or in-person office visits.

### 3. Data Collection

#### 3.1 Data sources and study setting

The patients will be enrolled from the operating room of nine China tertiary hospitals: Affiliated Hospital of Guangdong Medical University (Guangdong), First Affiliated Hospital of Sun Yat-sen University (Guangdong), Foshan First People's Hospital (Guangdong), First Affiliated Hospital of Zhengzhou University (Henan), The First Affiliated Hospital of Nanchang University (Jiangxi).

#### 3.2 Data collection tools and instruments

The data collection will be facilitated through a network-based data infrastructure, where in the potential predictor variables are comprehensively described in [Table 1](#). Further details can be accessed on the website <https://www.wjx.cn/>. Prior to sample inclusion, data collectors at all participation centers underwent mandatory homogenization training. The clinical follow-up will be conducted at 0.5, 2, 24, 48, and 72 hours post-surgical procedure, as well as at the three-month mark following the completion of the surgical procedure. The investigator has the flexibility to carry out these follow-ups either through ward visit, telephone communication or follow-up appointments for outpatient care.

**Table 1: Potential predictor variables**

Braden scale
1. Sensation
Completely limited: unresponsive (does not moan, flinch or grasp) to painful stimuli because of diminished level of consciousness or sedation OR a limited ability to feel pain over most of body

surface.
Very limited: responds only to painful stimuli; cannot communicate discomfort except by moaning or restlessness OR has a sensory impairment that limits the ability to feel pain or discomfort over half of the body.
Slightly limited: responds to verbal commands but cannot always communicate discomfort or need to be turned OR has some sensory impairment that limits ability to feel pain or discomfort in one or two extremities.
No impairment: responds to verbal commands; has no sensory deficit that would limit ability to feel or avoid pain or discomfort.
2. Skin moisture
Constantly moist: skin is kept moist almost constantly by perspiration, urine etc; dampness is detected every time patient is moved or turned
Moist: skin is often, but not always, moist; linen must be changed at least once a shift
Occasionally moist: skin is occasionally moist, requiring an extra linen change approximately once a day
Rarely moist: skin is usually dry; linen changed only at routine intervals.
3. Activity
Bedfast: confined to bed
Chairfast: ability to walk severely limited or nonexistent; cannot bear own weight and/or must be assisted into chair or wheelchair.
Walks occasionally: walks occasionally during day but for very short distances, with or without assistance; spends majority of each shift in bed or chair.
Walks frequently: walks outside the room at least twice a day and inside room at least once every 2h during waking hours.
4. Mobility
Completely immobile: does not make even slight changes in body or extremity position without assistance.
Very limited: makes occasional slight changes in body or extremity position but unable to make frequent or significant changes independently.
Slightly limited: makes frequent, though slight, changes in body or extremity position independently
No limitations: makes major and frequent changes in position without assistance
5. Nutritional status
Very poor: never eats a complete meal; rarely eats more than one-third of any food offered; eats two servings or less of protein (meat or dairy products) per day; takes fluids poorly; does not take a liquid dietary supplement OR is NPO and/or maintained on clear liquids or IV for more than 5 days.
Probably inadequate: rarely eats a complete meal and generally eats only about one-half of any food offered; protein intake includes only three servings of meat or dairy products per day; occasionally takes a dietary supplement OR receives less than optimum amount of liquid diet or fed by tube.
Adequate: eats over one-half of most meals; eats a total of four servings of protein (meat, dairy products) each day; occasionally refuses a meal but will usually take a supplement if offered OR is on a tube feeding or TPN regimen, which probably meets most of nutritional needs.
Excellent: eats most of every meal; never refuses a meal; usually eats a total of four or more servings of meat and dairy products; occasionally eats between meals; does not require supplementation.

6. Shear force
Problem: requires moderate to maximum assistance in moving; complete lifting without sliding against sheets is impossible; frequently slides down in bed or chair, requiring frequent repositioning with maximum assistance; spasticity, contractures or agitation leads to almost constant friction.
Potential problem: moves feebly or requires minimum assistance; during a move, skin probably slides to some extent against sheets, chair, restraints or other devices; maintains relatively good position in chair or bed most of the time but occasionally slides down.
No apparent problem: moves in bed and chair independently and has sufficient muscle strength to lift up completely during move; maintains good position in bed or chair at all times.
Waterlow scale
7. Gender
Male
Female
8. Age
14-49
50-64
65-74
75-80
81+
9. Skin type
Healthy
Tissue paper (thin/fragile)
Dry (appears flaky)
Oedematous (puffy)
Clammy (moist to touch)/pyrexia
Discoloured (bruising/mottled)
Broken (established ulcer)
10. Body Mass Index (BMI) Build/weight for height
Average – BMI 20-24.9
Above average – BMI 25-29.9
Obese – BMI > 30
Below average – BMI < 20
11. Nutritional Element
Unplanned weight loss in past 3-6 months
< 5% score 0, 5-10% score 1, >10% score 2
BMI >20 score 0, BMI 18.5-20 score 1, BMI < 18.5 score 2
Patient/ client acutely ill or no nutritional intake > 5 days
12. Tissue Malnutrition
Multiple organ failure/terminal cachexia
Single organ failure e.g., cardiac, renal, respiratory
Peripheral vascular disease
Anaemia (Hb < 80 g/L)
Smoking

13. Continence
Complete/catheterised
Incontinent urine
Incontinent faeces
Doubly incontinent (urine & faeces)
14. Mobility
Fully mobile
Restless/fidgety
Apathetic (sedated/depressed/reluctant to move)
Restricted (restricted by severe pain or disease)
Bedbound (unconscious/unable to change position/traction)
Chair bound (unable to leave chair without assistance)
15. Major surgery
On table > 6 hours
Orthopaedic/ below waist/spinal (up to 48 hours post op)
On table > 2 hours (up to 48 hours post op)
16. Neurological deficit
Motor/sensory
Diabetes
Paraplegia
Cardiovascular and cerebrovascular diseases/ multiple sclerosis (MS)/ cerebrovascular accident (CVA)
17. Medication
Long term/high dose steroid
Cytotoxic
Anti-inflammatory
Norton scale
18. Physical condition
Very bad
Poor
Fair
Good
19. Mental condition
Stupor
Confused
Apathetic
Alert
20. Activity
Bed
Chairbound
Walks with help
Ambulant
21. Mobility

Mobility	
Slightly limited	
Very limited	
Immobile	
22. Incontinent	
Doubly	
Usually (urine)	
Occasionally	
No	
Cubbin & Jackson scale	
23. Age	
<40	
40-55	
56-70	
>70	
24. Weight	
Average weight	
Obese	
Cachectic	
Any of above and oedema	
25. General skin condition	
Intact	
Red skin	
Grazed/excoriated/skin	
Necrosis/exuding	
26. Mental condition	
Awake and alert	
Agitated/restless/confused	
Apathetic/sedated but responsive	
Coma/unresponsive/unpurposeful movements	
27. Mobility	
Fully ambulant	
Walks with slight help	
Very limited/chairbound	
Immobile/bedrest	
28. Haemodynamic status	
Stable without inotropic support	
Stable with inotropic support	
Unstable with inotropic support	
Critical with inotropic support	
29. Respiration	
Spontaneous	
Continuous positive airway pressure (CPAP)/T-piece	

Mechanical ventilation
Breathless at rest/on exertion
30. Nutrition
Full diet + fluids
Light diet/oral fluids/enteral
Parenteral feeding
Clear IV fluids only
31. Incontinence
None/anuric/catheterised
Urine
Faeces
Urine + faeces
32. Hygiene
Competent in maintaining own hygiene
Maintaining own hygiene with slight help
Requires much assistance
Fully dependent
Munro scale
Preoperative Risk Factor Score
33. Nutritional state (Length of NPO status)
12 hours or <
>12 hours but <24 hours
>24 hours
34. Body Mass Index or weight
<30 kg/m  (normal)
30 kg/m  -35 kg/m  (underweight/obese)
>35kg/m  (morbidly obese)
35. Weight Loss (Weight loss in 30–180 days)
Up to 7.4% weight loss, no change or unknown
Between 7.5% and 9.9% weight loss
≥10% weight loss
36. Age
39 or <
40-59
60 or >
37. Mobility
Not limited, or slightly limited, moves independently
Very limited, requires transfer assistance
Completely immobile, requires full assistance
38. Comorbidity (Identify and add 1 point for each condition)
Smoking/Asthma/Hypertension/Diabetes/Vascular disease/respiratory disease
Intraoperative Risk Factor Score
39. Physical status/American Society of Anesthesiologists pre-anesthesia evaluation score

Healthy and mild systemic disease, no functional limitations
Moderate to severe systemic disease, some function limitation
Moderate to severe systemic disease, constant threat to life and functionally incapacitating or ASA >3
40. Anesthesia
Minimum alveolar concentration (MAC), local
Regional
General
41. Body temperature (98.6°F=37°C)
36.1°-37.8° (body temperature maintained)
>37.8° or <36.1° (+ or -2°) (fluctuated + or ->2°)
>37.8° or <36.1° (+ or - >2°) (maintained + or ->2°)
42. Hypotension
Absent or <10% change in blood pressure
Fluctuating or 11%-20% change in blood pressure
Persistent or 21%-50% change in blood pressure
43. Moisture (Skin under patient)
Remains dry
Some moisture
Pooled or heavy fluid
44. Support surface (Positioning aids, warming blanket, position change)
None/use of blanket over/stationary
Use of aids/blanket under/stationary
Shearing force/added pressure/variable position
45. Position (for surgical procedure)
Lithotomy
Lateral
Supine/Prone
Postoperative Risk Factor Score
46. Length of surgery (Total time from arrival to preoperative and departure from postoperative units)
Up to 2 hours
>2 hours & <4 hours
>4 hours
47. Blood loss
Up to 200 cc
201-400 cc
> 400 cc
Relevance of clinical nursing judgement as a contributing factor
48. Nurses are trained in surgical positions.
49. The nurse assumes the role of leading the surgical position.
50. The nurse executed the surgical positioning in accordance with the predetermined plan.

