### **Methods:**

We will use a pre-set observational assessment scale that consists of 24 indicators to construct the predictive model in this study. In addition to these pre-set indicators, the researchers will also collect other relevant indicators that they believe may contribute to the predictive model. Primary outcome was incidence of IAPI of any stage at 7 days from operating room admission. Secondary outcomes were in-hospital mortality (follow-up endpoint is 3 months after surgical procedure), surgical complication, and hospitalization costs. The prospective cohort study dataset is divided randomly into two

subsets: a training group (80% of the data) and an internal validation group (20% of the data). The training group is used for model development, while the internal validation group remains untouched until later stages. In model development, researchers can explore different variables and test various machine learning algorithms, such as logistic regression, artificial neural network (ANN), XGBoost, support vector machine (SVM), k-nearest neighbors (k-NN), naive Bayes, gradient boosting machines (GBM), AdaBoost, Gaussian mixture model (GMM), and support vector regression (SVR). They can train and optimize these models using the training dataset. After training the models on the training dataset, researchers can evaluate their performance using appropriate evaluation metrics (e.g., accuracy, precision, recall, F1-score, area under the receiver operating characteristics curve). Based on the evaluation results, we refine the model by tweaking hyperparameters, feature selection, or employing techniques like cross-validation or grid search. This iterative process aims to find the best-performing model configuration. Once the model is optimized using the training dataset, it is then evaluated on the internal validation dataset. This evaluation serves as an unbiased assessment of the model's performance on unseen data, providing an estimate of its ability to generalize. Based on the performance on the internal validation dataset, to choose the best-performing model as the final predictive model.

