## 51. Other variables (at the discretion of the nurse/doctor)

### 3.3 Schedule of Events

The events schedule comprised three sequential stages: recruitment and screening, baseline assessment, and outcome follow-up. The primary endpoint of this study is to evaluate the clinical outcomes three months post-surgery, its follow-ups should be office visits, but telephone contact will be allowed. Data collected during all follow-up visits will include IAPI, SSI, surgical complication, death. Original source documents must be submitted for any clinical events (death, IAPI, SSI, surgical complication, within 3 months).

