### **3.5 Data collection**

The clinical data of each surgical patient were collected by itinerant nurses who actively participated in the surgical procedure, and the data they collected were promptly submitted post-operation. Endpoint follow-up was conducted by dedicated personnel through telephone interviews, web-based data completion, or other appropriate methods.

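### Candidate predictor item 46 (Length of surgery) can close after the first IAPI checks, contradicts other sections of the plan, and no prediction time is stated

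*Combined protocol and SAP*

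**What the plan says.** - **Item 46 (section 3.2, Table 1).** It belongs to the postoperative part of the Munro scale, is headed Length of surgery, and is defined as "Total time from arrival to preoperative and departure from postoperative units". It is banded at 2 and 4 hours.
- **Item 51 (end of Table 1).** "Other variables (at the discretion of the nurse/doctor"). No measurement window is given.
- **Outcome.** The Abstract states "Primary outcome was incidence of IAPI of any stage at 7 days from operating room admission". Section 2.6 sets the checks: "The clinical follow-up will be conducted at 0.5, 2-, 24-, 48-, 72-hours and 7 days post-surgery". Table 2 marks IAPI at every follow-up time from 0.5 hours. Section 2.5.1 describes IAPI as "most occurring within 1-3 days postoperatively".
- **Predictor timing elsewhere.** Section 2.5.3 takes physiological indicators from the 24 hours before surgery, "while other intraoperative observation indicators", which expressly include surgical time and blood loss, are recorded during the operation. Table 2 marks predictors in the baseline column and at no follow-up time. Section 3.5 says of the nurses who took part in the operation that "the data they collected were promptly submitted post-operation".
- **Comparison.** Section 4.2.2 compares every model with the Braden, Waterlow, Norton, Cubbin & Jackson and Munro scales.

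No section says at what moment the score is to be calculated, or that predictors must be fixed before the first skin check.

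**The concern.** A prediction model should use only what is known when the prediction is made. Item 46, as defined, is known only when the patient leaves the postoperative unit. By then one or two outcome checks may have taken place, and an injury seen at those checks could itself have lengthened the stay.

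The planned safeguards would not reveal this. Recursive feature elimination (section 4.2.1) keeps what improves predictive performance, so it would tend to favour a contaminated item. The random 80/20 split and the repeated cross-validation give training and test data the same recording window, so any leakage appears equally in both.

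There is also a data-quality problem. Depending on which section a site follows, item 46 could hold the operating time, the time elapsed when the form was submitted, or the full perioperative stay.

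Finally, the Braden and Norton items contain nothing intraoperative, while the candidate set does. Without a stated prediction time, a gain over those two scales mixes better modelling with later information.

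**Working it through.** The plan gives no figure on this point, so the check compares time windows and then uses an illustration on assumed values.

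**1. Windows side by side**

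| Source | When the predictor is fixed |
|---|---|
| Table 1, item 46 | Departure from the postoperative unit |
| Section 2.5.3, surgical time | During surgery |
| Table 2 | Baseline |
| Section 3.5 | Submitted promptly after the operation, no cut-off given |
| Table 1, item 51 | Not stated |

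These cannot all hold. Table 2 cannot be literally right for any intraoperative item, and a form submitted promptly after surgery may precede the end of item 46.

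**2. Overlap with the checks**

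Item 46 closes after the 0.5 h check if the postoperative-unit stay exceeds 0.5 h, and after the 2 h check if it exceeds 2 h. The documents give no stay length. Assume a lognormal stay with median m and log-SD 0.4, so that P(stay > t) = 1 − Φ(ln(t/m)/0.4):

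| Assumed median stay | Past the 0.5 h check | Past the 2 h check |
|---|---|---|
| 0.5 h | 50% | <1% |
| 1 h | 96% | 4% |
| 2 h | >99% | 50% |

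**3. Change of band without any leakage**

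An assumed patient with 0.5 h preoperative time, 1.5 h surgery and 1.0 h in the postoperative unit scores 0.5 + 1.5 + 1.0 = 3.0 h. That is the middle band, whereas surgical time alone falls in the lowest.

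**4. Possible effect on AUC**

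The 13.9% incidence comes from section 4.1; everything else is assumed. Surgery time is lognormal (median 1.8 h, log-SD 0.6) and preoperative time uniform from 0.25 to 0.75 h. The log-odds of IAPI rise by 0.25 per hour of surgery. There are 300,000 simulated patients. Feedback means that 10% to 50% of IAPI cases stay 0.5 to 1 h longer because of the injury. Banded surgical time alone has an AUC of 0.582.

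| Median stay | Item 46, no feedback | Weakest feedback (10%, 0.5 h) | Strongest feedback (50%, 1 h) |
|---|---|---|---|
| 0.5 h | 0.575 | 0.584 | 0.649 |
| 1 h | 0.567 | 0.574 | 0.641 |
| 2 h | 0.544 | 0.549 | 0.596 |

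Feedback raises the AUC of item 46 by between 0.549 − 0.544 = 0.005 and 0.649 − 0.575 = 0.074. Against surgical time, item 46 ranges from 0.544 − 0.582 = −0.038 to 0.649 − 0.582 = +0.067. These are single-predictor values; they do not show what would happen to the full model.

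**The case against.** The strongest defence is that the plan already constrains timing. Section 2.5.3 places surgical time and blood loss within the operation, Table 2 shows no predictor at any follow-up time, and section 3.5 asks for prompt submission. If those sections are followed, nothing observed after the first check enters item 46. This stands in part: the defect is a contradiction between one item's definition and three other sections, not a declared intention to use later data. It does not remove the problem, because the item's own definition is what a person completing the form will read.

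Three stronger readings are tempting, and the documents support none of them.

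- **That item 15 has the same fault.** A reader might infer this from "On table > 2 hours (up to 48 hours post op"). The label most naturally says how long the category applies. Time on table is fixed when surgery ends, and a later injury cannot change it.
- **That Table 1 predictors in general run past the outcome.** Among the 51 items, item 46 is the only clear case. Item 51 is a possibility because it has no window.
- **That performance is necessarily inflated.** This needs an early IAPI to prolong the unit stay, which no section states. The plan expects most IAPI on days 1-3, normally after departure from the unit, so only injuries seen at the earliest checks could feed back. Without feedback the wider window weakens the predictor.

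On comparators, it is fair to reply that Munro includes intraoperative items and Waterlow includes time on table, so comparison with similar-stage information is already planned. That answers the point for Munro in particular, but not for Braden and Norton.

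**Conclusion.** The point holds for item 46, with item 51 as an open door. Item 46 can close after the 0.5 h check, and sometimes after the 2 h check. It contradicts sections 2.5.3 and 3.5 and Table 2, and no prediction time exists to settle which applies. That much follows from the definitions alone.

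The consequence is conditional: possible inflation if an early IAPI prolongs the stay, possible dilution if it does not. The range of −0.038 to +0.067 in single-predictor AUC rests wholly on assumed stay lengths and feedback. Its upper end needs half of all IAPI cases to affect the unit stay, which sits uneasily with the timing that the plan expects.

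This is more than a missing detail, because a stated predictor definition admits information from after the first check that the planned validation cannot detect. It should be corrected before the model is fitted.

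**What to change.** 1. State the prediction time, for example end of surgery or leaving the operating room. Admit to the new model only predictors fixed by then and recorded, with a time stamp, before the first IAPI check. Apply this to item 51 as well.
2. For the new model, replace item 46 with the surgical time already recorded under section 2.5.3. Keep the full-stay version only to score the Munro comparator.
3. Correct Table 2 so that preoperative and intraoperative predictors have separate columns, consistent with sections 2.5.3 and 3.5.
4. For the Braden and Norton comparisons, add a model restricted to preoperative items, or state that any gain over them includes later information. Munro remains the comparator using similar-stage information.

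The cost is a few definitions, a time-stamp field and one extra model fit. The reported AUC may change slightly in either direction. If data have already been collected, the substitution in step 2 needs only the recorded surgical time.
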